
2. Objectives (include all primary and secondary objectives)

Primary objective: Determine the interaction of expectancy effects and nicotine dose on behavioral economic demand for reduced-nicotine cigarettes. Demand will be evaluated using an incentivized demand task with experienced outcomes to provide experimental rigor. We hypothesize lower demand (via intensity and elasticity) for “very low” labels and low nicotine content cigarettes, with the lowest demand when in combination.

Secondary objective: Determine the interaction of expectancy effects and nicotine dose on subjective effects and smoking topography for reduced-nicotine cigarettes. Participants will sample the study cigarette at the start of each session and complete craving, mood, withdrawal, and subjective drug effect measures before and after smoking. Smoking topography will also be collected during cigarette administration to determine if expectancy and dose impact how one smokes (another primary way cognitive or pharmacological effects can impact smoking). Based on prior research, we hypothesize lower positive subjective effects and lower puff volume for “very low” labels and reduced-nicotine cigarettes with the lowest values for their combination.

3. Background (briefly describe pre-clinical and clinical data, current experience with procedures, drug or device, and any other relevant information to justify the research)

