Primary Analysis: Low nicotine expectancy and low nicotine dose will result in lower demand with lowest demand in combination: Demand variables will be computed and transformed if non-normal (e.g., log-transform). Analyses will use a 2x2 repeated measures ANOVA with the within-subject factors of expectancy (“average” and “very low”) and dose (15.8 mg/g and 0.4 mg/g). Hypothesis 1 will be supported by significant main effects indicating significantly lower demand under “very low” expectancy and 0.4 mg/g conditions. A significant interaction would also indicate different-than-additive effects of expectancy and dose. Such an interaction is plotted in Figure 3 with hypothetical data of a greater reduction in demand intensity by nicotine content under the “very low” expectancy condition.

Secondary Analysis: Low nicotine expectancy and low nicotine dose will result in lower positive subjective effects (H2) and lower puff volume (H3) with lowest values in combination. A 2x2 ANOVA will also be used for puff topography and subjective effect measures with similar predictions as Hypothesis 1. Measures with pre- and post-cigarette administration measures will use a 2x2x2 ANOVA including a within-subject factor of time. We expect less reduction in withdrawal and craving with low nicotine expectancy and low nicotine dose indicated by significant interactions with time.

Sample Size Justification: With respect to power, simulation of a 2x2 repeated measure ANOVA based on estimates from preliminary demand data (e.g., nicotine dose effect, SD) identified 82% power to detect a main effect under additive effects. More generally, the sample provides 80% power to detect a medium-large bivariate within-subject effects ($d_z = 0.66$). This project is considered a pilot project and therefore we have focused on a feasible sample size to generate signals of the behavioral relevance for expectancy in reduced-nicotine policy to inform scientific rationale for future projects. These findings will also provide evidence for the feasibility of within-session procedures with incentivized consequences for rapidly evaluating demand of experimental commodities, thereby serving as preliminary “proof-of-concept” data for a variety of proposals evaluating the reinforcing effects of novel experimental commodities. We will enroll up to 25 participants that complete the study to ensure that at least 20 provide fully systematic data on primary demand outcomes.

d. Early stopping rules.

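### Section 6c counts significant main effects as support for lowest demand in the combination, which fails under a strongly less-than-additive interaction; the detectable size of the interaction named as primary objective is not given

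*Combined protocol and SAP*

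**What the plan says.** Section 2 opens with "Primary objective: Determine the interaction of expectancy effects and nicotine dose on behavioral economic demand". Its hypothesis is lower demand for the very low label and for the low-nicotine cigarette, "with the lowest demand when in combination".

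Section 6c (Primary Analysis) repeats the combination prediction, specifies a 2x2 repeated measures ANOVA and gives the decision rule: "Hypothesis 1 will be supported by significant main effects indicating significantly lower demand under" the very low label and the 0.4 mg/g dose. The interaction comes next: "A significant interaction would also indicate different-than-additive effects of expectancy and dose". Figure 3 is described as showing "hypothetical data of a greater reduction in demand intensity by nicotine content under the" very low label, which is a greater-than-additive shape. No comparison of the combined cell with either single-factor cell is planned.

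In the Secondary Analysis, positive subjective effects (H2) and puff volume (H3) carry the same ordering claim, "lower puff volume (H3) with lowest values in combination", to be analysed "with similar predictions as Hypothesis 1".

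The Sample Size Justification gives 82% power for a main effect under additive effects, and 80% power for a within-subject effect of d_z = 0.66. It calls the project a pilot with a feasibility-based sample size.

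**The concern.** A main effect averages over the levels of the other factor. It shows that the label lowers demand on average and that the dose lowers demand on average. It does not compare the cell with both low features against the cells with only one. If one factor alone already brings demand down as far as it will go, both main effects can be clear while the combination adds nothing. Read literally, 6c would then report the whole of Hypothesis 1 as supported, including its combination part.

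There is a second, smaller gap. Section 2 names the interaction as the primary objective, but the power text does not say what size of interaction the sample can detect.

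**Working it through.** **Inputs from the documents.** Analysable N = 20; 82% power for one main effect; 80% power at d_z = 0.66 (all Section 6c).

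**Assumptions.** Two-sided 0.05, because 6c states no level; equal and independent errors (SD 1) in the four cells; label and dose main effects equal unless stated. The inputs to the plan's simulation are not given, so the main effect is back-solved from the 82%.

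**1. The plan's own figure.** Paired t-test, noncentral t, 19 df: d_z = 0.66 at N = 20 gives power 0.7995. The stated 80% reproduces. Power of 82% at N = 20 needs d_z = 0.678.

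**2. When main effects imply the ordering.** Let D and E be the dose and label main effects (reductions), and I the difference of simple effects, positive when less than additive.
- Combination below very low/15.8 by D − I/2.
- Combination below average/0.4 by E − I/2.
- So the combination is lowest only if I < 2 × min(D, E).

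Additive (I = 0) and greater-than-additive (I < 0) effects always satisfy this. Mildly less-than-additive effects do too.

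**3. Counterexamples.** Cell means in the order average/15.8, average/0.4, very low/15.8, very low/0.4.
- 10/5/5/5: D = [(10 − 5) + (5 − 5)]/2 = 2.5, and E is the same. I = 5 − 0 = 5 = 2 × 2.5. The combination equals each single factor.
- 10/6/6/7: D = [(10 − 6) + (6 − 7)]/2 = 1.5, and E is the same. I = 4 − (−1) = 5 > 3. The combination is above both.

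**4. How often the rule is met.** Simulation with 40,000 trials, N = 20, D = E = 0.678.

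| True pattern | Both main effects significant | Interaction significant | Combination significantly below both single-factor cells |
|---|---|---|---|
| Additive (combination lowest) | 0.676 | 0.050 | 0.363 |
| 10/5/5/5 type (combination equal to each) | 0.669 | 0.820 | 0.004 |
| 10/6/6/7 type (combination above both) | 0.676 | 0.997 | 0.000 |

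A repeat with 100,000 trials gave 0.673, 0.671 and 0.673 in the first numeric column.

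In the 10/5/5/5 case, 0.120 of trials meet the rule with no significant interaction. The observed cell means seldom warn the reader in those trials: the combination mean is visibly not lowest in only 0.006 of all trials.

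With the label effect at 0.5, 0.75 and 1.25 times the dose effect, the rule is met in 0.249, 0.477 and 0.778 under additivity. It is met in 0.246, 0.474 and 0.774 when dose has no effect under the very low label. Requiring both contrasts in the second case gives a false claim in 0.0004, 0.0015 and 0.0085.

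**5. What d_z = 0.66 means for the interaction.** The interaction is a one-degree-of-freedom contrast, so 0.66 applies to its difference score at N = 20. Its raw size depends on the variance structure.
- Cell error SD 1 only: main-effect contrast SD = √(4 × 1/4) = 1 and interaction SD = √4 = 2. Detectable interaction: 0.66 × 2 = 1.32 main-contrast SDs.
- If dose and label effects also vary between people with SD 1: main-contrast SD = √(1 + 1) = 1.41 and interaction SD = 2, a ratio of 1.41. Detectable interaction: 0.66 × 1.41 = 0.93 main-contrast SDs.

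The documents do not say which structure applies, so this range cannot be narrowed from outside.

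**The case against.** The strongest reply is that the plan works in a setting where its rule is sound. Power is computed under additivity, Figure 3 is greater than additive, and in both cases two main effects do imply that the combination is lowest. The failure needs a large interaction in the opposite direction, and the interaction is tested in the same ANOVA. That the rule is met equally often in the two cases follows from holding the main effects fixed. All of this stands, and it limits the harm. It does not close the gap: 6c does not make additivity a condition of the rule or tie Hypothesis 1 to the interaction test. A significant interaction also does not say which cell is lowest.

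Four stronger readings are tempting and are not supported.
- *Main effects can never show the ordering.* They do, whenever I < 2 × min(D, E).
- *The interaction goes untested.* It is in the planned ANOVA, and the synopsis and background state the aim as both independent and interactive effects. Section 2 is loosely worded.
- *The gap extends to withdrawal and craving.* The text there is "We expect less reduction in withdrawal and craving with low nicotine expectancy and low nicotine dose indicated by significant interactions with time". It predicts less reduction with each factor and does not claim an extreme value for the combination.
- *The stated power is wrong.* The 82% is correctly labelled as a main effect under additivity, and the 0.66 reproduces.

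The pilot status excuses modest power. It does not make a rule test an ordering that it does not examine.

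**Conclusion.** The concern holds in limited form. The ANOVA is valid; the rule attached to it does not secure the combination part of Hypothesis 1, nor the matching parts of H2 and H3, when the interaction is strongly less than additive. In the 10/5/5/5-type case the rule is met about 67% of the time, the interaction test flags about 82% of trials, and about 12% meet the rule with no flag. These figures rest on N = 20, equal main effects back-solved to 82% power, and equal independent cell errors. The algebra in step 2 needs none of those assumptions.

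On power, the gap is one of reporting: the plan does not say what raw interaction its d_z = 0.66 represents, although Section 2 makes the interaction primary. This should be fixed, because the change is small and the present rule can yield a wrong statement.

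**What to change.** In Section 6c:
- Let the two main effects support the separate label and dose claims only.
- For H1, H2 and H3, base the combination claim on two paired contrasts: very low/0.4 against average/0.4, and very low/0.4 against very low/15.8. Report both with 95% CIs beside the interaction estimate and its 95% CI.
- Call the combination claim supported only when both contrasts show significantly lower values. Otherwise report cell means and CIs as a pilot signal.
- Judge Q0 and α separately, with the sign reversed for α, and say which metric supports the claim.
- State that the 82% refers to a single main effect and that d_z = 0.66 also applies to the interaction difference score. Take the joint power for both main effects, and the raw detectable interaction, from the sponsor's own simulation and not from the assumptions used here.

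In Section 2, state the objective as independent and interactive effects, so that it matches 6c.

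The cost is wording and two extra contrasts per outcome, with no added participants or measurements. The downside is that the combination claim becomes harder to support: about 36% power per metric if effects are additive and equal, under the assumptions above.

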screening will be scheduled for in-person screening at our research unit. Laboratory screening will include health history, drug history, and physical examination. Those passing full screening will participate in 1 practice session with procedures identical to experimental sessions but using the participant's own-brand cigarette. This practice session will serve to acclimate the participant to the study procedures, account for practice effects, and provide data for exploratory comparisons with own-brand cigarette data. Following practice sessions, each participant will complete 4 experimental sessions in which nicotine content (15.8 mg/g versus 0.4 mg/g) and expectancy (participant instructed "average" versus "very low" nicotine; see details below) are manipulated as within-subject variables. The full combination of sessions will be 15.8 told average; 15.8 told low; 0.4 told average; 0.4 told low completed in a randomized order.

Practice and Experimental Session Timeline

Participants will complete 4 experimental sessions lasting about 4 hours. Upon arrival to the laboratory, carbon monoxide will be collected to verify 8-hour abstinence as indicated by a CO <50% of the value obtained a screening (e.g., Mercincavage et al., 2016). A battery of subjective effect measures will be collected prior to cigarette administration including the Minnesota Nicotine Withdrawal Scale (MNWS; Toll et al., 2007), the Questionnaire on Smoking Urges (QSU; Cox et al., 2001), and the Positive and Negative Affect Scale (PANAS; Watson et al., 1988) measuring nicotine withdrawal, cigarette craving, and mood, respectively.

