Participants will then smoke one of that session's cigarette (15.8 mg/g or 0.4 mg/g). Participants will be instructed that this cigarette is either "the same level of nicotine as your usual brand" or "a very low level of nicotine compared to your usual brand" to harmonize with prior work on expectancy (Mercincavage et al., 2016). This manipulation will be necessary for the expectancy variable and success of the study protocol. A thorough debriefing about the study will occur at study completion or if a participant discontinues participation early. Dose will be double-blind such that neither research staff nor participants know the dose. Expectancy will be single-blind such that research staff who collect outcome assessments will not know the exposure participants receive (i.e., a separate member of research staff will deliver the manipulation). Participants will have 10 minutes to smoke the whole experimental cigarette. Topography will be collected including measures of total puff volume, mean puff volume, mean puff duration, mean inter-puff interval, mean maximum flow rate, and number of puffs using existing topography equipment. Subjective effect measures (MNWS, QSU, and PANAS) will be collected again following the 10-minute smoking period. Subjective effect measures about the experimental cigarettes will also be collected (i.e., 100-point visual analog scale drug effect measures such as "Strength" and "Satisfaction"). Physiological measures (e.g., CO) will be collected prior to and following cigarette administration.

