Demand tasks will be analyzed for derived and curve-observed measures. Derived measures include demand intensity (Q0; consumption at unconstrained price) and demand elasticity (a measure of sensitivity of consumption to changes in price) and will be computed using the exponential demand equation $\text{LogQ} = \text{Log Q0} + k(e^{-\alpha Q0C}) - 1$ (Hersh & Silberberg, 2008). The independent variable C is cost (price/cigarette), the dependent variable Q is consumption (cigarettes purchased at a particular price), the scaling parameter k indicates the range of LogQ in the observed data. Free parameters are Q0 (demand intensity) and α (demand elasticity). Should zero-dense data be observed, a modified exponentiated form of the demand equation will be considered (Koffarnus et al., 2015; Strickland et al., 2016). Observed measures include Pmax (price at maximum consumption), Omax (maximum consumption), and breakpoint (Breakpoint-1; the price of last non-zero demand).

b. Secondary outcome variables. Descriptions of Outcome Measures

Subjective Effect Measures

Subjective effect measures will include a measure of nicotine withdrawal (MNWS), smoking craving (QSU), mood (PANAS), and cigarette subjective experience (Drug Effect Questionnaire). These measures will be collected upon arrival to the laboratory (i.e., immediately prior to cigarette administration) and following the 10-minute standardized smoking period. All measures will be scored using standard procedures.

Smoking Topography

Six measures of smoking topography will be collected including: total puff volume, mean puff volume, mean puff duration, mean inter-puff interval, mean maximum flow rate, and number of puffs (Higgins et al., 2018). These measures will be collected during the 10-minute standardized cigarette smoking period using a custom smoking topography system currently in use in our laboratory.

c. Statistical plan including sample size justification and interim data analysis.

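### Optional improvement, not an error: MNWS, QSU and PANAS are tested as raw pre-to-post change; a prespecified adjustment for each session's pre-cigarette score could add power at small risk

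*Combined protocol and SAP*

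**What the plan says.** The secondary objective (section 2) has participants "complete craving, mood, withdrawal, and subjective drug effect measures before and after smoking". Section 4a (Practice and Experimental Session Timeline) schedules the MNWS, QSU and PANAS in each session: "A battery of subjective effect measures will be collected prior to cigarette administration", and then "Subjective effect measures (MNWS, QSU, and PANAS) will be collected again following the 10-minute smoking period". Section 6b repeats the timing: "These measures will be collected upon arrival to the laboratory (i.e., immediately prior to cigarette administration) and following the 10-minute standardized smoking period". Each participant receives all four label-by-dose combinations, in random order (section 4a, General Overview: "0.4 told low completed in a randomized order").

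The analysis is in section 6c, Secondary Analysis: "Measures with pre- and post-cigarette administration measures will use a 2x2x2 ANOVA including a within-subject factor of time". The expected result is read from the time terms: "We expect less reduction in withdrawal and craving with low nicotine expectancy and low nicotine dose indicated by significant interactions with time". No covariate is named there or elsewhere.

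This point is confined to the MNWS, QSU and PANAS. Section 6b also lists the Drug Effect Questionnaire among the measures taken before and after smoking, but section 4a describes the cigarette ratings only after it.

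**The concern.** With two-level factors, each condition-by-time term in the planned ANOVA is a test on a contrast of raw change. That is efficient only if the best coefficient for the pre score is close to 1. If the pre score predicts the post score less than one-for-one within a person, subtracting all of it adds noise. The sample is about 20 to 25 people, so lost efficiency cannot easily be recovered by recruiting more.

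The stake is limited to precision on secondary outcomes. The scores are already scheduled in every session, so an adjusted analysis needs no new data. It should be chosen before the data are seen, because picking between change and adjusted results afterwards would be selective.

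**Working it through.** **Inputs from the plan.** Section 6c (Sample Size Justification): d_z = 0.66 with 80% power, at least 20 participants with systematic demand data, up to 25 completers. The d_z is a general within-subject figure, not one for these scales, and the 20 refers to the demand outcomes. Both are borrowed as an anchor.

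**Assumptions.** Two-sided alpha 0.05 (not stated). r = within-person correlation of the pre and post condition contrasts, 0.2 to 0.8. k = SD of the post contrast divided by SD of the pre contrast, 0.75 to 2. Stable differences between people already cancel in the ANOVA, so the usual between-person pre/post correlation is not the relevant r.

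**Step 1: the plan's own figure.** Paired t-test, noncentral t with N − 1 df and noncentrality 0.66 × √N. At N = 20 this is 0.66 × 4.472 = 2.95 on 19 df, power 79.95%, which agrees with the plan ("the sample provides 80% power to detect a medium-large bivariate within-subject effects"). At N = 25 it is 88.6%.

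**Step 2: the ANOVA tests raw change.** In a simulated 20-person data set, F for expectancy × time was 1.2749 and F for the three-way term was 11.4069. Each equals the squared t from a one-sample test on the matching contrast of post minus pre.

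**Step 3: variances**, with the pre-contrast SD set to 1:

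- Var(change) = k² + 1 − 2rk
- Var(adjusted) = k²(1 − r²)
- Difference = (1 − kr)², which is zero only when kr = 1
- Ratio adjusted/change = k²(1 − r²) / (k² + 1 − 2rk)

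Example, k = 1, r = 0.4: 0.84 / 1.20 = 0.70. Example, k = 1.25, r = 0.8: 0.5625 / 0.5625 = 1.00, no gain.

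**Step 4: power of the adjusted test at N = 20.** The post contrast is regressed on the pre contrast and the intercept is tested on N − 2 = 18 df. The noncentrality is 0.66 × √(N / ratio), reduced for estimating the slope (on average the variance rises by a factor 1 + 1/(N − 3) = 1.059). Results are averaged over simulated pre contrasts. The change test is 79.95% in every cell.

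| k | r = 0.2 | r = 0.4 | r = 0.6 | r = 0.8 |
|---|---|---|---|---|
| 0.75 | 98.5% | 97.1% | 95.6% | 95.1% |
| 1 | 93.8% | 89.8% | 85.8% | 81.6% |
| 1.25 | 88.8% | 84.1% | 80.0% | 77.5% |
| 1.5 | 85.2% | 80.7% | 77.8% | 79.4% |
| 2 | 81.0% | 78.0% | 78.1% | 85.8% |

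Five of the 20 cells gain more than 10 points: all four at k = 0.75, and k = 1 with r = 0.2. Five lose power.

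**Step 5: worst case.** At kr = 1 the variances are equal, and only the cost of estimating the slope remains: 77.5% against 79.95% at N = 20 (about 2.5 points), and 87.1% against 88.6% at N = 25 (1.5 points).

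**Step 6: effects that differ between people.** An added between-person SD of τ in the effect turns k into √(k² + τ²) and r into rk / √(k² + τ²). With τ = 1, a pair that would have had k = 0.75 has an actual k of √(0.5625 + 1) = 1.25, and r of 0.2 to 0.8 becomes 0.12 to 0.48. The table is in actual k and r, so it already covers this case.

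**Step 7: validity.** In simulations with N = 20 and 25 and k from 0.75 to 1.5, type I error was 0.044 to 0.055 for both tests.

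**The case against.** The planned analysis tests what the plan predicts. The expectation is worded as a smaller reduction, and the ANOVA tests reduction directly. The study is a pilot sized for feasibility, these outcomes are secondary, the craving and withdrawal expectation carries no hypothesis number, and mood has no directional prediction for this test. All of that stands, and it is why this is only something to consider. It does not make raw change the better test: with session order randomized and the pre score taken before exposure, both analyses target the same condition effect.

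The benefit also cannot be established from the documents. r and k are absent, the effect size is borrowed, and even the sign of the gain is unknown. Requiring 8 hours of abstinence before every session might narrow the spread of pre scores and raise k, towards the rows where little is gained; the documents do not settle this. This objection stands in full.

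The remedy estimates nine slopes (three scales by three contrasts) from about 20 people. True, but the cost of each slope is what Step 5 bounds.

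Finally, that the pre battery precedes the label is inferred from the order of description in section 4a. Section 6b places it before the cigarette, which is not quite the same. This stands and is part of the fix.

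A reader might infer that the ANOVA is biased or wrong, or that adjustment would reliably add 10 points or more. The documents support neither: the ANOVA is valid, and gains of that size need particular values of r and k that nobody has reported here.

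**Conclusion.** A cheap improvement to consider, with medium confidence, limited to the secondary MNWS, QSU and PANAS analyses. The gain is large only when k × r is well below 1 with k about 1 or less, or when k × r is well above 1 with k large. When k × r is near 1 the gain is small or slightly negative. On the stated anchor, the N = 20 grid runs from 77.5% to 98.5% against 79.95% for the planned test.

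The loss bound applies to the contrast regression and to this effect size. The conclusion rests on the assumed two-sided 0.05, the borrowed d_z, and the pre score being free of any influence of that session's label. The primary demand analysis, H3 and the plan's power statement do not change. A sponsor who keeps change scores for simplicity would not be making an error.

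**What to change.** Add to section 6c, for the MNWS, QSU and PANAS only:

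> For each participant, the expectancy, dose and interaction contrasts will be computed from the four post-cigarette scores and from the four pre-cigarette scores. Each post contrast will be regressed on the matching uncentred pre contrast, and the intercept will be tested on N − 2 degrees of freedom. The 2x2x2 ANOVA will be kept as a sensitivity analysis and to test the overall effect of time.

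The covariate must be each session's own pre score, because a single baseline per person cancels out of the within-person contrasts.

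State in section 4a that the pre battery is completed before the label is delivered. If it is not, the pre score is not a pre-exposure value and should not be used in this way. Reporting the observed r and k for each scale would help later studies, which this pilot is meant to inform.

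Cost: SAP wording and a few lines of code, one error degree of freedom per contrast, and at worst about 2.5 points of power at N = 20 (1.5 at N = 25). No extra data are needed.
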